6. INVESTIGATIONAL PLAN

6.1 Overall Study Design and Plan – Description

This is a multicenter study to assess the efficacy and safety of taliglucerase alfa (60 units/kg) in previously untreated subjects of any age with Type 3 GD. For the purposes of this study, subjects receiving no Gaucher-specific medications for at least 12 months will be considered “untreated”. Subjects will receive an IV infusion of taliglucerase alfa every 2 weeks for 12 months. Subjects who are treated in centers where home therapy is the SOC will be allowed to switch from site to home treatment at the discretion of the PI but after no less than 3 uneventful infusions at the site. At the end of the 12-month treatment period, eligible subjects will be offered enrollment in an open-label extension study if taliglucerase alfa is not commercially available.

6.2 Discussion of Study Design and Choice of Control Group(s)

Type 3 GD is a very rare genetic orphan disease. This study will not have a placebo control group because it would be unethical to deny patients the possibility to improve their symptomology with an ERT that has been proved efficacious and safe, not only for Type 1 GD in many countries but also for Type 3 GD in a small number of countries. Thus, all subjects will receive the investigational product in this study.

The parameters chosen as endpoints for this study are the most relevant parameters to GD and allow a significant and relevant evaluation of improvement as a result of treatment for 12 months. Improvement in the clinical manifestations of the disease leads to the achievement of the therapeutic goals of GD treatment in the medical community, which are improved fatigue and decreased risk for morbidities.

6.3 Selection of Study Population

6.3.1 Inclusion Criteria

For inclusion into the trial, subjects are required to fulfill all of the following criteria:

1. Male or female of any age; however, if female:
 - must be using contraception if of childbearing potential or must be surgically sterile
 - must not be lactating
2. Diagnosis of Type 3 GD by enzyme and sequence analysis; and confirmed by the Medical Monitor.
3. Splenomegaly at least 5 x multiples of normal (MN).
4. Treatment-naïve.

6.3.2 Exclusion Criteria

Any of the following is regarded as a criterion for exclusion from the trial:

1. Type 2 GD.
2. Presence of myoclonic seizures.
3. At least one allele of:
 - N370S (N409S in recent nomenclature)
 - R496H (R535H in recent nomenclature)
4. Presence of calcification in heart valves or arteries in echocardiography.
5. Presence of untreated iron, folic acid, vitamin B₁₂ deficiency and/or hypothyroidism. (Resolved anemia is not an exclusion criterion.)
6. Presence of human immunodeficiency virus (HIV), hepatitis B surface antigen (HBsAg), and/or hepatitis C virus (HCV) infections.
7. Splenectomy and bone marrow transplantation.
8. Presence of any medical, emotional, behavioural, or psychological condition that in the judgment of the Investigator would interfere with the subject's compliance with the requirements of the study.
9. Any other disorder that may interfere with the results of the efficacy endpoints.
10. Pregnancy or breastfeeding.
11. Currently taking another investigational drug for any condition or any therapeutic drug for Gaucher disease.
12. The subject and/or subject's parent(s) or legal guardian(s) are unable to understand the nature, scope, and possible consequences of the study.
13. Any medical history of food/drugs allergy.

6.3.3 Removal of Subjects from Study

Reasons for permanent discontinuation include the following:

1. The subject experiences two or more Grade 3 toxicities or one or more Grade 4 toxicity considered by the Investigator associated with taliglucerase alfa treatment (see [Section 8.2.1: Adverse Events](#); and [Appendix 14.5: WHO Common Toxicity Criteria](#))
2. The subject experiences progressive hypersensitivity or severe hypersensitivity will be treated appropriately and may be withdrawn from the study, at the discretion of the treating Investigator and/or Medical Monitor (see [Appendix 14.2: Infusion Rate Algorithm](#); and [Appendix 14.3: Taliglucerase Alfa Hypersensitivity Evaluation and Treatment Algorithm](#))
3. The subject, or subject's parent or guardian, requests to discontinue treatment
4. Investigator feels that it is not in the best interest of the subject to continue treatment and/or the Investigator believes that the subject can no longer be compliant with the requirements of the study
5. Deteriorating clinical condition, which the Investigator decides additional treatments would be needed

For any discontinuation, the Investigator will obtain all required details and document the date and the main reason for the premature discontinuation. If the reason for discontinuation is an adverse event, the specific event or the main laboratory abnormality will be recorded in the case report form (CRF). The Investigator will make thorough efforts to document the outcome. The Investigator will attempt to continue to follow the subject for the full duration of the study or at least for 30 days following discontinuation. If circumstances prevent the subject from completing all visits, every attempt will be made to complete all procedures listed in [Section 9.2.11](#) for Visit 27.

6.3.4 Replacement Policy

Withdrawn subjects will not be replaced.

7. STUDY PRODUCT

7.1 Study Medication Supply

Reconstitution of each taliglucerase alfa vial (212 units) with sterile water for injection (5.1 mL) yields a final volume of 5.3 mL human taliglucerase alfa (40 U/mL), which provides a withdrawal volume of 5.0 mL (200 units). The solution must be mixed gently until clear.

7.2 Description of Study Product

Human taliglucerase alfa is a purified recombinant, plant cell-expressed glucocerebrosidase, which is described in detail in the taliglucerase alfa Prescribing Information ([Appendix 14.1](#)).

Each 200 unit vial contains the following lyophilized ingredients:

- 212 units of taliglucerase alfa

- 195 mg mannitol
- 35 mg sodium citrate
- 0.53 mg polysorbate 80, NF

7.3 Description of Comparator Product

Not applicable.

7.4 Study Drug Administration

Taliglucerase alfa will be administered over 1 to 2 hours (the total volume to be prepared and infused is 100-120 mL + 20 mL saline flushing of the system) for initial infusions in all subjects. Tolerability will be determined by vital signs taken 30 minutes after starting the infusion and symptoms during the infusion and for one hour after the infusion in the clinic and also by telephone contact the day after the first infusion. If this initial rate of infusion is well tolerated, the infusion rate may be increased up to 2.0 mL/min (120 mL/hr) to deliver the volume of reconstituted enzyme plus 20 mL saline flush over 1 to 2 hours for all subsequent dose administrations (see [Appendix 14.2: Infusion Rate Algorithm](#)).

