2.2 Preparation Instructions

ELELYSO should be reconstituted, diluted, and administered under the supervision of a healthcare professional.

Each vial of ELELYSO provides 200 units of taliglucerase alfa and is intended for single use only. Do not use the vial more than one time. The reconstitution and dilution steps must be completed using aseptic technique.

ELELYSO should be reconstituted with Sterile Water for Injection and diluted with 0.9% Sodium Chloride Injection, USP, to a final volume of 100 mL to 200 mL, and delivered by intravenous infusion.

Prepare ELELYSO according to the following steps. Use aseptic technique.

- Determine the number of vials to be reconstituted based on the patient's weight and the recommended dose of 60 units/kg, using the following calculations (1-3):
 - Total dose in units = Patient's weight (kg) x dose (units/kg)
 - Total number of vials = Total dose in units divided by 200 units/vial
 - Round up to the next whole vial.

b. Remove the required number of vials from the refrigerator. Do not leave these vials at room temperature longer than 24 hours prior to reconstitution. Do not heat or microwave these vials.

c. Reconstitute each vial of ELELYSO with 5.1 mL of Sterile Water for Injection to yield a reconstituted product with a concentration of 40 units/mL and an extractable volume of 5 mL. Upon reconstitution, mix vials gently. DO NOT SHAKE. Prior to further dilution, visually inspect the solution in the vials; the solution should be clear and colorless. Do not use if the solution is discolored or if foreign particulate matter is present.

d. Withdraw the calculated dose of drug from the appropriate number of vials and dilute with 0.9% Sodium Chloride Injection, USP, to a final volume of 100 to 200 mL.

i. For pediatric patients, a final volume of 100 to 120 mL should be used.

ii. For adult patients, a final volume of 130 to 150 mL may be used. However, if the volume of reconstituted product alone is equal to or greater than 130 to 150 mL, then the final volume should not exceed 200 mL.

e. Mix gently. DO NOT SHAKE. Since this is a protein solution, slight flocculation (described as translucent fibers) occurs occasionally after dilution.

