2.3 Administration Instructions

After reconstitution and dilution, the preparation should be administered via intravenous infusion and filtered through an in-line low protein-binding 0.2 μ m filter.

- For pediatric patients: An initial infusion rate of 1 mL/minute should be used. After tolerability to ELELYSO is established, the infusion rate may be increased, but should not exceed the maximum recommended infusion rate of 2 mL/minute. The total volume of the infusion should be delivered over a minimum of 60 minutes.

- For adult patients: An initial infusion rate of 1.2 mL/minute should be used. After tolerability to ELELYSO is established, the infusion rate may be increased, but should not exceed the maximum recommended infusion rate of 2.2 mL/minute. The total volume of the infusion should be delivered over a minimum of 60 minutes.

As ELELYSO contains no preservative, the product should be used immediately once reconstituted. If immediate use is not possible, the reconstituted product may be stored for up to 24 hours at 2 to 8 °C (36 to 46 °F) under protection from light or up to 4 hours at 20 to 25 °C (68 to 77 °F) without protection from light. The diluted product may be stored for up to 24 hours at 2 to 8 °C (36 to 46 °F) under protection from light. Storage of the reconstituted product and the diluted product should not exceed a total of 24 hours. Do not freeze. Discard any unused product.

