14.2 Appendix 2: Infusion Rate Algorithm

[figure not shown]
The infusion rate (IR) may be adjusted according to individual subject symptoms and signs. The assumptions with respect to adverse experiences to the infusion are:

1. Most of the subjects will tolerate the infusion without any special symptom or event. The infusion rate may be increased over time to the maximal rate 2.0 mL/minute (or 120 mL/hour) only after discussion with the Medical Monitor (an infusion duration of 1 hour).
2. Subjects presenting symptoms and signs of **severe** hypersensitivity will be evaluated according to the WHO Drug Toxicity criteria and there may be a discontinuation of treatment according to the protocol.
3. Subjects may present signs and symptoms that will respond to reducing of the infusion rate and may not appear at the next infusion.
4. Tolerability and the subject specific infusion rate will be assessed and decided by the Investigator according to vital signs and clinical status of the subject.

Definitions to be applied regarding tolerability of infusions are as follows:

Good Tolerability	Partial Tolerability	Poor Tolerability
Infusion was performed without signs and symptoms (such as burning, pruritus, flushing, discomfort, or change in vital signs).	Signs and symptoms appeared during the infusion and resolved after slowing infusion rate or at the end of the infusion.	Signs and symptoms meeting the definitions of WHO Grade 1 or 2 toxicity responding to reduction of infusion rate or responding to treatment (example, antihistamine for urticaria).

The specific algorithm to be followed is below.

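### Protocol 7.4 allows a one-hour first infusion, a pace Appendix 14.2 holds back for later use after Medical Monitor discussion; separately, its 120 mL limit cannot hold the dose above 80 kg

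*Protocol*

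**What the plan says.** **Section 7.4, first infusion.** "Taliglucerase alfa will be administered over 1 to 2 hours". The same sentence gives the volume as 100–120 mL plus a 20 mL saline flush and applies it to initial infusions in every subject. No starting rate in mL/min appears in the text.

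**Section 7.4, later infusions.** If the initial rate is tolerated, it may rise to at most 2.0 mL/min, with the reconstituted enzyme plus flush again given over 1 to 2 hours, "for all subsequent dose administrations". This sentence refers to Appendix 14.2 but does not mention the Medical Monitor.

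**Appendix 14.2.** The rate may rise over time to the maximal 2.0 mL/min (120 mL/hour) "only after discussion with the Medical Monitor (an infusion duration of 1 hour". The algorithm figure is not visible in the copy reviewed.

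**Appended US label (Appendix 14.1, label sections 2.1 to 2.3).**
- Overall duration: 60 to 120 minutes.
- Children: "An initial infusion rate of 1 mL/minute should be used", and "For pediatric patients, a final volume of 100 to 120 mL should be used".
- Adults: "An initial infusion rate of 1.2 mL/minute should be used", in 130–150 mL, or up to 200 mL when the reconstituted drug alone reaches 130–150 mL.
- Both: "After tolerability to ELELYSO is established, the infusion rate may be increased".

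**Dose and eligibility.** The dose is 60 units/kg (Synopsis) at 40 units/mL after reconstitution (Section 7.1). Section 6.3.1 admits any age, and the eligibility criteria set no weight limit.

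**The concern.** The first infusion is a subject's first exposure to the enzyme, and Appendix 14.2 treats the fastest infusion as something to be reached later, with a second opinion. Section 7.4 gives the first infusion the same 1-to-2-hour window as the later, faster ones. A site that reads only 7.4 could schedule a 60-minute first infusion and be at the rate the appendix holds back.

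The volume rule raises a second, separate question. Section 7.4 applies to all subjects the volume that the label gives for children. A heavy adult's dose may not fit in it.

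What is at stake is infusion safety and clear instructions to sites. Label section 5.1 reports hypersensitivity reactions in 21 of 72 patients (29%), including 2 consistent with anaphylaxis. Sample size, power and the efficacy analyses do not depend on any of this.

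**Working it through.** **Step 1. Reproduce the plan's own figure.** Appendix 14.2 equates 2.0 mL/min with 120 mL/hour and a one-hour infusion. 2.0 × 60 = 120 mL, and 120 / 2.0 = 60 min. The figures agree with each other.

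**Step 2. Average rate implied by Section 7.4's window.** Rate = volume / time.

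| Volume | Over 60 min | Over 120 min |
|---|---|---|
| 100 mL, no flush | 100/60 = 1.67 mL/min | 0.83 mL/min |
| 120 mL, no flush | 120/60 = 2.0 mL/min | 1.0 mL/min |
| 100 + 20 mL flush | 120/60 = 2.0 mL/min | 1.0 mL/min |
| 120 + 20 mL flush | 140/60 = 2.33 mL/min | 1.17 mL/min |

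Section 7.4 puts the flush inside the infused total, and for later doses explicitly inside the 1 to 2 hours, so the last two rows are the natural reading. They are at or above the 2.0 mL/min maximum. At that maximum, 140 mL takes 140 / 2.0 = 70 min, so it cannot be given in an hour at all. Only for 100 mL with the flush left out does the average stay below 2.0; there the conflict is over the one-hour duration, not the rate. The two-hour end raises no difficulty.

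**Step 3. Set against the other text.** Section 7.4 speaks of an initial rate that may be increased to 2.0, so that rate must be lower than 2.0. Appendix 14.2 allows 2.0 only over time and after discussion. The one-hour lower bound for the first infusion fits neither.

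**Step 4. First-infusion time if the label's starting rate is held throughout.**
- Children, 1 mL/min: 100–120 min; with flush 120–140 min.
- Adults, 1.2 mL/min: 100/1.2 = 83 min to 120/1.2 = 100 min; with flush 120/1.2 = 100 min to 140/1.2 = 117 min.

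**Step 5. Volume of drug.** 60 units/kg ÷ 40 units/mL = 1.5 mL/kg.
- Largest weight that 120 mL can hold, with no diluent: 120 / 1.5 = 80 kg.
- 87.0 kg (top of the weight range for Type 1 adults on 60 units/kg, label Table 3): 130.5 mL, which is 10.5 mL over the limit.
- 73.5 kg (median of that group): 110.25 mL, which fits.
- 50.4 kg (heaviest child on 60 units/kg in the same table): 75.6 mL, which fits.
- Label adult volumes: 150 mL holds up to 100 kg; 200 mL up to 133.3 kg.

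**Step 6. Does the two-hour limit survive the adult volumes?** As an illustration, take 30 min at 1.2 mL/min (36 mL), leaving 90 min.
- 150 mL: (150 − 36)/90 = 1.27 mL/min; with flush (170 − 36)/90 = 1.49.
- 200 mL: (200 − 36)/90 = 1.82 mL/min; with flush (220 − 36)/90 = 2.04, just above the 2.0 maximum.

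The limit therefore holds for 200 mL only if the flush is left out of it.

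**The case against.** **The figure.** The 14.2 algorithm is where one would expect a starting rate, and it cannot be seen. This stands. A reader might infer that the protocol has no safe starting rate; the documents do not support that, and the missing figure is not a fault of the plan. What remains is that a lower rate in the figure would not remove 7.4's one-hour bound, and that the Medical Monitor condition is in visible text.

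**The label's window.** The label gives treatment-naïve patients 60 to 120 minutes with no exception for the first dose, so 7.4's window is the label's own. This stands, and it keeps the point small. The label, however, pairs the window with numerical starting rates, which the text of 7.4 does not.

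**The cross-reference.** Section 7.4 cites 14.2, so the Medical Monitor condition may be taken as included. This is fair for later doses. The citation sits in the sentence on later doses, not in the one that sets the first-infusion window.

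**Two stronger readings to avoid.** First, that any one-hour infusion must start above the label's rate. Not so: leaving out the flush, 20 min at 1 mL/min and 40 min at 2.0 mL/min gives 20 + 80 = 100 mL, and the label lets the rate rise once tolerated. Second, that a rise must wait for 7.4's vital signs ("Tolerability will be determined by vital signs taken 30 minutes after starting the infusion"). No visible text makes that reading a step-up point within an infusion, and flow-chart footnote h limits vital signs to before and after infusion unless an adverse event occurs.

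**Rarity of heavy subjects.** Type 3 disease usually begins between infancy and adolescence (Section 4.1), at most 15 subjects are planned, and no document shows a Type 3 patient above 80 kg. This stands. The label's adult volume is also permissive, and 7.4 states 100–120 mL only for initial infusions, so one should not infer that heavy adults would be underdosed throughout.

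**Safeguards.** One-hour observation, the next-day call, the investigator's control of the rate (14.2) and the rule to stop at any listed sign (14.3) limit the harm.

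**Conclusion.** Two wording faults hold on the visible text.

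1. Section 7.4's one-hour lower bound for the first infusion conflicts with Appendix 14.2. The implied average is 2.0–2.33 mL/min with the flush counted and 1.67–2.0 mL/min without it, against a 2.0 mL/min maximum that is to be reached only over time and after Medical Monitor discussion.
2. The 100–120 mL volume for initial infusions in all subjects cannot hold the dose above 80 kg. This can occur because any age is eligible, but it is probably rare.

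This is a minor consistency and safety point that is worth correcting. It assumes that the unseen figure does not override the text of 7.4. The label gives no breakdown of reactions by infusion rate, so the added risk cannot be quantified. No efficacy result is affected.

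**What to change.** Amend Section 7.4 as follows.

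1. Start the first infusion at the appended label's rate, 1 mL/min for children and 1.2 mL/min for adults, or at the 14.2 figure's rate if that is lower. Do not schedule a first infusion at 60 minutes.
2. State that 2.0 mL/min is subject to the Medical Monitor condition in Appendix 14.2.
3. Keep 100–120 mL for pediatric subjects. For adults, allow the label's 130–150 mL, and up to 200 mL when the drug alone requires it.
4. Say whether the two-hour limit includes the flush. Either exclude the flush or allow the limit to be extended when needed. This matters for 200 mL in adults (2.04 mL/min in the illustration above) and for 120 mL in children held at 1 mL/min (140 min with flush).

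The cost is protocol wording and a longer first visit: about 83–120 min for 100–120 mL if the starting rate is held, or about 100–140 min with the flush, instead of a possible 60. No change to the SAP is needed.

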- ^e Molecular analysis will be done locally (if not done before), and a confirmation from Central Laboratory (Centogene) will be done using the CentoCard.
- ^f HDL, Phosphate inorganic and cholesterol assessments, which are taken at screening, should not be repeated at baseline, if done within a period of 1 month.
- ^g ALT and AST assessments are enough if activated ALT and activated AST are done on site (or the way around).
- ^h Vital signs to be done once on screening visit, from baseline till visit 27; to be done only pre and post infusion, and as needed if an AE occurs during infusion.

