6. DEXA
7. Taliglucerase alfa infusion
8. Adverse event evaluation

The following procedures will be performed after taliglucerase alfa dosing:

1. Observe the subject clinically for a minimum of 1 hour post-dosing.
2. Evaluate vital signs pre and post infusion, and as needed if an AE occurs during infusion. Evaluate the injection site.
3. A follow up telephone call with the subject and/or parent or guardian will be held the day after the infusion.

The subject and/or parent or guardian will be reminded of the date of the next visit.

9.2.3 Visits 2 – 5 (Weeks 2, 4, 6, and 8 ± 3 Days)

Subjects will receive their taliglucerase alfa infusion at their selected medical center. The following procedures will be performed post-dosing:

1. Observe the subject clinically for a minimum of 1 hour post-dosing.
2. Evaluate vital signs pre and post infusion, and as needed if an AE occurs during infusion.
3. Evaluate the injection site.

Adverse events and concomitant medications will be recorded at each visit.

Subjects will only receive transfusions at the medical center where they will be followed up and treated. The procedures to be followed will depend on local standards of care and procedures established at the medical center. Minimally, safety data (vital signs, adverse events, concomitant medications) will be recorded at each bi-weekly treatment with taliglucerase alfa administered at the medical center.

The subject and/or parent or guardian will be reminded of the date of the next visit.

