9.2.4 Visit 6 (Week 10 ± 3 Days)

Subjects will receive their taliglucerase alfa infusion at their selected medical center. The following procedures will be performed post-dosing:

1. Adverse event evaluation.
2. Concomitant medications.
3. Vital signs pre and post infusion, and as needed if an AE occurs during infusion.

The subject and/or parent or guardian will be reminded of the date of the next infusion/visit.

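### Protocol 7.4 judges tolerability of the initial infusions partly on vital signs at 30 minutes, but Table 1 footnote h restricts vital signs to before and after the infusion unless an adverse event occurs

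*Protocol*

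**What the plan says.** Protocol 7.4 (Study Drug Administration) covers the initial infusions in all subjects, each given over 1 to 2 hours. It states: "Tolerability will be determined by vital signs taken 30 minutes after starting the infusion and symptoms during the infusion". The same sentence adds symptoms for one hour afterwards and a telephone call the day after the first infusion. If the initial rate is well tolerated, it may be raised to at most 2.0 mL/min. Appendix 14.2 repeats the link between vital signs and rate: the subject's "infusion rate will be assessed and decided by the Investigator according to vital signs and clinical status of the subject".

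The schedule says something else. Footnote h to Table 1 (Protocol 9.1) states that vital signs from baseline to Visit 27 are "to be done only pre and post infusion, and as needed if an AE occurs during infusion". Section 9.2.2 (Visit 1) and Section 9.2.3 (Visits 2 to 5) both read "Evaluate vital signs pre and post infusion, and as needed if an AE occurs during infusion". Section 9.2.2 also carries two other parts of the 7.4 rule: "Observe the subject clinically for a minimum of 1 hour post-dosing" and "A follow up telephone call with the subject and/or parent or guardian will be held the day after the infusion". It does not list a 30-minute reading.

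SAP 3.5.3 describes vital signs every 30 minutes in subjects who tolerated earlier infusions, and otherwise every 15 minutes in the first hour. That matches neither protocol text.

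**The concern.** The 30-minute vital signs are a named input to a safety decision, namely whether the infusion may run faster next time. Footnote h rules that reading out in an uneventful infusion. It does more than stay silent, because it contains the word *only*.

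A site that builds its worksheets from the flow chart and visit lists would observe the subject for an hour and make the call, but would have no vital signs from during the infusion when it judged tolerability. A change in blood pressure or pulse that caused no symptoms and had settled by the end of the infusion would go unseen. The adverse-event exception would not help, because without a reading there would be nothing to prompt it.

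The setting gives this some weight. The prescribing information in Appendix 14.1 (section 5.1) reports hypersensitivity reactions in 21 of 72 patients (29%) and anaphylaxis in 2 of 72 (3%). It says the anaphylactic reactions occurred during infusion and lists hypotension among their signs.

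**Working it through.** There is no plan figure to reproduce. The check is a comparison of texts, with one short piece of arithmetic on timing.

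**Inputs**
- Infusion length T: 60 to 120 minutes (Protocol 7.4).
- Reading that the tolerability rule uses: 30 minutes after the start (Protocol 7.4).
- Scheduled vital signs when no adverse event occurs: before and after the infusion, baseline to Visit 27 (footnote h).
- Visit-list timing: before and after, plus as needed for an adverse event (9.2.2 and 9.2.3).

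**Step 1. Can the 30-minute reading count as a pre- or post-infusion reading?** No. With T between 60 and 120, 0 < 30 < T, so it always falls inside the infusion.

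**Step 2. Does footnote h cover the initial infusions?** Yes. Its range is baseline to Visit 27. The protocol does not say how many infusions are initial, but the count starts at Visit 1, which is inside that range.

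**Step 3. Does the exception in footnote h restore the reading?** No. It applies when an adverse event occurs during the infusion. The 7.4 reading is meant for every initial infusion, including those without an event.

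**Step 4. Do the early visit lists supply it?** No. The parts of the 7.4 rule compare with 9.2.2 as follows:

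| Part of the 7.4 rule | In the 9.2.2 list? |
|---|---|
| Vital signs at 30 minutes | No; pre and post only |
| Symptoms during the infusion | Not listed |
| Symptoms for one hour afterwards | Yes, as clinical observation |
| Call the day after the first infusion | Yes |

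Section 9.2.3 has the same vital-sign timing and the one-hour observation.

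**Step 5. What interval goes unmeasured?**
- Without the reading, the gap between the pre and post readings is at least T, so at least 60 to 120 minutes.
- With the reading, the longest gap within the infusion is max(30, T − 30). For T = 60 this is max(30, 30) = 30 minutes. For T = 120 it is max(30, 90) = 90 minutes.

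Scheduled in-infusion vital signs in an uneventful initial infusion are therefore 1 under 7.4 and 0 under footnote h.

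**The case against.** Much of the case against a larger finding stands.

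- **A reader might infer that every infusion-visit section contradicts 7.4.** All ten sections, 9.2.2 to 9.2.11, use pre/post timing and none lists a 30-minute reading. But 7.4 concerns only the initial infusions, so the later lists would not be expected to carry it. The word *only* stands in footnote h alone. The visit lists are also not exhaustive: 9.2.2 omits symptom watching during the infusion, which nobody would take as cancelling it. The conflict is between 7.4 and footnote h; the early visit lists fail to resolve it.
- **A reader might infer that no in-infusion vital signs will be taken.** The documents do not show that. Section 7.4 is itself a protocol instruction, and some sites will follow it. The gap arises where a site follows footnote h instead.
- **The algorithm could not be seen.** Appendix 14.2 says "The specific algorithm to be followed is below", but the figure is missing from the text available. It may give timings. If so, sites would have another instruction to take the reading, although footnote h would still exclude it in words.
- **The clinical scenario is hypothetical.** No passage shows that symptom-free changes resolving before the end of infusion occur or matter. The prescribing information in Appendix 14.1 allows a rate increase once tolerability is established and sets no timing for vital signs.
- **SAP 3.5.3 adds little.** A SAP does not direct site procedures. The SAP also departs from the protocol elsewhere, for example on home therapy (after 3 months, against at least 3 uneventful infusions), so version drift is a plausible explanation.

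None of this reconciles a required 30-minute reading with a footnote that permits only pre and post readings.

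**Conclusion.** The inconsistency is real and minor. In an uneventful initial infusion, 7.4 calls for a 30-minute reading and footnote h excludes it. A site following footnote h would decide on the rate without the in-infusion vital signs that 7.4 names.

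The effect is confined to safety conduct. Safeguards that remain are symptom observation, the next-day call after the first infusion, discussion with the Medical Monitor before the maximal rate (Appendix 14.2) and the hypersensitivity algorithm (Appendix 14.3). A reader might go on to infer that trial results are at risk. The documents do not support that: vital signs enter no efficacy endpoint, and SAP 6.7.3 lists them and summarises them descriptively only at baseline and Months 3, 6, 9 and 12.

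Confidence is high on the conflict in wording and lower on its practical consequence. The consequence depends on which text sites follow and on what the Appendix 14.2 figure contains. Because the protocol does not define how many infusions are initial, no share of affected infusions can be given.

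**What to change.** Amend footnote h so that, for the initial infusions and until tolerability at the rate is established, vital signs are also taken 30 minutes after the start. Make the same change in 9.2.2, and in 9.2.3 as far as those visits count as initial. Align SAP 3.5.3 with the resulting protocol schedule, and check that any timings in the Appendix 14.2 figure agree.

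Deleting the 30-minute reading from 7.4 would also remove the conflict. That is the weaker choice, because the rate decision would then rest on no scheduled in-infusion vital signs. If the restriction in footnote h was deliberate, the protocol should say so and restate the tolerability rule to match.

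The cost is wording in the protocol and SAP, possibly one CRF field, and one quick reading per initial infusion, which 7.4 already requires.
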